Subgroup Name	Levels	Additional Details, if applicable		
		(140 - age) * baseline weight (kg) * (0.85 if		
		female) /		
		(72 * baseline serum creatinine [mg/dL])		

K. Data Display Characteristics

Data displays produced for this study will include three types—summary tables, data listings, and figures. Unless stated otherwise, data listings will be produced for all recorded data as well as derived variables. Summary tables will be produced as specified in following sections. Figures will be produced when specified in sections to follow.

Listings will be ordered by phase, treatment (dose and schedule), cohort, patient number, and nominal visit. When expedient, additional levels of ordering hierarchy may reflect subsets of assessments within patient. Data listings will not display patient initials.

Tables will be organized differently based on the purpose of the data analysis being performed: interim safety analyses or formal interim analysis or final analysis. Data snapshots taken for the purpose of safety analysis (regulatory reporting, IB update, etc.) will be organized as outlined in Appendix 3. Table generation for interim futility and efficacy analyses as well as final analyses will be organized as specified in Appendix 3.

The summary statistics displayed will be a function of the type of data associated with the summarized assessment. Unless stated otherwise in relevant sections to follow, continuous data will be summarized with the number of non-missing values, mean, standard deviation, minimum, median, and maximum. Categorical data will be summarized with the number of non-missing values and the numbers of values equal to each of the possible values. Percentages of patients with each of the possible values will be calculated from the number of patients in the corresponding analysis set, unless stated otherwise. Some continuous variables may also be grouped into categorical levels and evaluated in frequency tables.

L. Blinded Review of Data

Not applicable for this study, as it is open label.

VII. Baseline Patient Characteristics and Disposition

A. Disposition

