Differentiation syndrome (DS) is a risk of drugs in this class. While many of the symptoms of differentiation syndrome are non-specific and best judged by the treating clinician, in the spirit of the article by Montesinos et al. (2009), and using methodology outlined by Norsworthy et al. (2020), candidate cases of DS will be summarized. This analysis will be conducted for IA2 only, and not for the final study reporting.

The number of patients with an investigator reported AE of DS will be summarized.

In addition, candidate cases of DS will be summarized based on AE data and also leukocyte count results from the laboratory data set. AE preferred terms will be summarized into categories representing possible symptoms of DS as per the table below, and tabulated by the number of patients experiencing an AE in the category in the first 90 days and 180 days post first dose.

Candidate DS AESI Symptom Category	AE Preferred Terms
Dyspnoea	Acute respiratory distress syndrome Acute respiratory failure Cardiopulmonary failure Cardio-respiratory distress Cough Dyspnoea Dyspnoea exertional Dyspnoea at rest Orthopnea Productive cough Respiratory distress

Pulmonary infiltrates or	Acute interstitial pneumonitis
Pleuropericardial effusion	Acute lung injury
1	Acute pulmonary oedema
	Acute respiratory distress syndrome
	Atypical pneumonia
	Bilateral pulmonary infiltrates
	Generalized oedema
	Interstitial pneumonitis
	Localized oedema
	Lower respiratory tract infection
	Lower respiratory tract inflammation
	Lung infiltration
	Non-cardiogenic pulmonary oedema
	Pericardial effusion
	Preumania
	Pneumonitis
	Pneumonitis
	Pulmonary infiltration NOS
	Pulmonary congestion
	Pulmonary congestion
	Pulmonary toxicity
	Tumonary toxicity
Kidney injury	
	Acute kidney injury
	Anuria
	Blood creatinine abnormal
	Blood creatinine increased
	Cardiorenal syndrome
	Hepatorenal failure
	Prerenal failure
	Renal failure
	Renal failure acute
	Renal function test abnormal
	Renal impairment
	Renal injury
TT / '	Creatinine value >26.52 μ mol/L or >1.5x baseline value in the lab dataset
Hypotension	Hypotension
	Orthostatic hypotension
	Blood pressure decreased
	Blood pressure systolic low
	Blood pressure diastolic decreased
	Any systolic blood pressure in vital signs data set < 90 mmHg
Fever	Pyrexia
	Febrile bone marrow aplasia
	Febrile neutropenia
	Temperature in vital signs data set $> 38.3^{\circ}$ C
Weight gain	Capillary leak syndrome
-0 0	Fluid overload

Fluid retention
Generalized oedema

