Hydraemia
Hypervolaemia
Oedema
Oedema peripheral
Weight increased
Weight (any value > 5 kg from baseline from vital signs data)

Candidate cases of DS will be identified based on patients having: any 2 or more AESI categories from the table above occurring concomitantly. Concomitant is defined for AESIs as AE start dates within 7 days of each other. Two or more AESI can comprise a DS episode. Repeat DS episodes are separated by > 14 days between the start dates of the AESIs.

The number of patients with candidate cases who have concomitant leukocytosis will be summarized. Concomitant leukocytosis is defined as having AE PT of "Leukocytosis," "Hyperleukocytosis," or "White blood cell count increased," or having laboratory results showing leukocyte count > 10 G/L within 7 days before or after AESI.

Candidate cases will be reviewed by an adjudication committee (details are contained within a separate DS Adjudication Committee charter). Committee members will review the patient cases and adjudicate which cases are DS, and the number of episodes of DS that each patient experienced. The number and percentage of patients who have a committee-adjudicated case of DS will be tabulated.

Of the cases adjudicated as having DS, the following summaries will be presented:

- The number of patients with multiple episodes of DS will be tabulated.
- The number of patients with concomitant leukocytosis will be tabulated.
- The number of patients experiencing severe and moderate DS will be tabulated. If a patient has a reported AE of differentiation syndrome, the severity will be assessed via CTCAE grade, with severe being grade 3/4/5, and moderate being grade 2. If they did not have an investigator-reported AE of differentiation syndrome, then severe is defined as experiencing more than 3 DS AESI categories concomitantly, and moderate is defined as experiencing 2 or 3 DS AESI concomitantly as per Montesinos (2009). These will be tabulated within the first 90 days post first dose, and the first 180 days post first dose.
- The number and percentage of patients reporting at least one DS AESI will be summarized by those occurring during the first 90 and 180 and days post first dose.
- The median time to onset of the DS episode (the first DS AESI for adjudicated cases) will be calculated, along with the 1st and 3rd quartiles of time to onset and the range.
- The number and percentage of patients who also had a best overall response of CR or CRh will be tabulated

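### The IA2 differentiation-syndrome screen counts any creatinine above 26.52 µmol/L (0.3 mg/dL) as kidney injury, which nearly every patient exceeds, and gives that trigger no date rule

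*SAP*

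**What the plan says.** SAP VIII.B, under the differentiation-syndrome (DS) heading, groups AE terms into six symptom categories. Some categories also have a trigger from the laboratory or vital-signs data. The relevant rules are:

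- **Kidney injury, laboratory trigger:** "Creatinine value >26.52" µmol/L, or ">1.5x baseline value in the lab dataset".
- **Weight gain, same table:** "Weight (any value > 5 kg from baseline from vital signs data".
- **Candidate case:** at least two categories present concomitantly.
- **Concomitance:** "Concomitant is defined for AESIs as AE start dates within 7 days of each other". Repeat episodes are likewise separated by the start dates of the events.
- **Leukocytosis (not a symptom category):** a laboratory result counts if it shows "leukocyte count > 10 G/L within 7 days before or after AESI".
- **Severity of an adjudicated case with no investigator-reported DS event:** "severe is defined as experiencing more than 3 DS AESI categories concomitantly"; two or three categories is moderate.
- **Time to onset:** taken from the first qualifying event of an adjudicated case.
- **Scope:** "This analysis will be conducted for IA2 only, and not for the final study reporting".

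An adjudication committee working under a separate charter decides which candidates are DS and how many episodes each patient had. A listing shows the criteria that made each patient a candidate.

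**The concern.** A creatinine of 26.52 µmol/L is far below the level of an adult with normal renal function, so as an absolute cut-off it does not identify kidney injury. Three features of the text suggest that words for an increase were left out: the figure is a round 0.3 mg/dL, it is paired with a multiple of baseline, and the weight row of the same table is written as a change from baseline.

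The second gap concerns dates. Concomitance is defined by AE start dates, and a laboratory value has none. The SAP dates leukocyte results, and in VIII.C it restricts the liver flags to post-baseline values with 7-day windows. Creatinine gets neither rule. The blood-pressure, temperature and weight triggers from the vital-signs data have the same gap.

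At stake are the candidate count and its listing, the kidney row of the category counts at 90 and 180 days, the moderate/severe split, and time to onset. These describe a syndrome that protocol Section 5.5.1 calls life-threatening in its full form.

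**Working it through.** **Inputs.** The trigger and the rules above come from SAP VIII.B. The clearance formula and the normal limit of 90 mL/min come from SAP VI.J. Chemistry days come from Appendix 1 of each document. The conversion factor of 88.4 µmol/L per mg/dL and the patient profiles are assumptions.

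**1. Unit conversion.** 26.52 / 88.4 = 0.300 mg/dL.

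**2. Creatinine at normal clearance.** Rearranging the SAP formula, creatinine (mg/dL) = (140 − age) × weight × (0.85 if female) / (72 × clearance). At 90 mL/min the denominator is 6480.

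| Profile | Calculation | mg/dL | µmol/L | Multiple of 26.52 |
|---|---|---|---|---|
| Man, 70 y, 75 kg | 70 × 75 / 6480 | 0.810 | 71.6 | 2.7 |
| Woman, 70 y, 65 kg | 70 × 65 × 0.85 / 6480 | 0.597 | 52.8 | 2.0 |
| Woman, 80 y, 60 kg | 60 × 60 × 0.85 / 6480 | 0.472 | 41.7 | 1.6 |

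To fall to the cut-off, these patients would need clearances of 243, 179 and 142 mL/min. Over a grid of ages 40 to 90, weights 50 to 90 kg and both sexes, creatinine at 90 mL/min runs from 29.0 to 122.8 µmol/L, always above the cut-off. The clearance at the cut-off runs from 98 to 417 mL/min.

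**3. Redundancy of the second limb.** The 1.5-fold limb can fire alone only if the value is at most 26.52 and also above 1.5 × baseline. That needs a baseline below 26.52 / 1.5 = 17.68 µmol/L (0.20 mg/dL).

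**4. What a rise from baseline would require.** The trigger becomes creatinine above the smaller of baseline + 26.52 and 1.5 × baseline. The two limbs cross where 0.5 × baseline = 26.52, at 53.04 µmol/L.

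- Baseline 40: trigger above 60.0.
- Baseline 60: trigger above 86.5.
- Baseline 80: trigger above 106.5.

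Under the printed text all three meet the trigger with no change at all.

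**5. Reach of the trigger under different date rules.** Scheduled chemistry falls on these days:

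- Protocol Appendix 1: 1, 5, 8, 12, 15, 19, 22, 26, 29, 36, 43, 50, 57, 71, 85, 113, 169.
- SAP Appendix 1: the same to day 50, then 57, 85, 113, 141, 169.

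| Date rule | Days 1–90 within 7 days of a qualifying sample | Days 1–180 |
|---|---|---|
| Every sample, protocol schedule | 90/90 (100%) | 92 + 15 + 15 = 122 (68%) |
| Every sample, SAP schedule | 77/90 (86%; gap on days 65–77) | 64 + 4 × 15 = 124 (69%) |
| First post-dose sample only (day 5) | 12/90 (13%; days 1–12) | 12/180 (7%) |
| AE start date required | 0 | 0 |

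Day 5 is used as the first post-dose sample because SAP VI.A treats a Cycle 1 Day 1 laboratory sample as baseline.

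**6. Effect on classification when the trigger is on and no genuine renal criterion is met.**

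| Genuine non-renal categories | Counted as | Consequence |
|---|---|---|
| 1 | 2 | Newly a candidate |
| 2 | 3 | Still moderate |
| 3 | 4 | Moderate becomes severe |
| 4 or more | 5 or more | No change |

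**The case against.** The strongest reply is that little depends on this.

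- **Scope.** The analysis is descriptive and confined to IA2, so rewording the SAP changes no later table. This stands as a limit on importance. It does not settle whether the IA2 results were affected, and the SAP's Summary of Changes itself calls IA2 pivotal.
- **Direction.** The literal rule contains the presumed intended one, so it can only widen the screen. No true case is lost, and adjudication should remove false candidates. This stands for the adjudicated DS count; the separately reported investigator count is also unaffected. It does not protect the candidate summary, the severity rule or onset. The committee's described task is to decide on DS and the number of episodes, not to confirm each category.
- **Strict reading.** Since concomitance needs AE start dates, a bare creatinine result might never count, and the effect would be nil. That reading is possible, but it would leave the laboratory trigger with no function in selecting candidates. The spread from 0 to 100% is itself evidence that the text does not fix the result.
- **Unseen sources.** The cited methodology, the adjudication charter or the program may hold the intended definition. That is fair, and the intent of 26.52 is an inference. However, protocol Section 9.2.4.2 says the methods for finding candidate cases will be fully described in the SAP.
- **Narrowness.** A shift from moderate to severe needs an adjudicated case with no investigator-reported DS event, exactly three genuine non-renal categories, no genuine renal criterion, and the trigger active at that time. The documents give no basis for saying how often that happens.

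**Conclusion.** The concern holds. As printed, the absolute creatinine limb does not discriminate: across the assumed profiles, every patient at 90 mL/min is above it, and the 1.5-fold limb adds nothing unless baseline is below 17.68 µmol/L. That conclusion rests on the standard unit conversion and the SAP's own formula.

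The consequence is less certain because it depends on how IA2 dated laboratory triggers. With sample dates, the kidney category is active on 86% to 100% of the first 90 days, and the two-category rule in effect becomes a one-category rule. With a first-exceedance rule, the reach is 13%. With AE start dates only, it is zero.

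This should be corrected and checked, but it is bounded. The analysis is for IA2 only, at most one of the six category counts (kidney) is affected, and neither the adjudicated nor the investigator-reported DS count is automatically inflated. No primary endpoint or hypothesis test is involved.

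**What to change.** 1. Restate the kidney laboratory trigger as an increase in creatinine of more than 26.52 µmol/L from baseline, or a value above 1.5 times baseline. The sponsor should confirm that this is what was intended.
2. State which date a creatinine or vital-sign trigger takes (for example first, any or worst qualifying post-baseline result) and its window for the 7-day rule, as is already done for leukocyte counts.
3. Check what the IA2 program coded. If it was the literal text, rerun candidate selection, the moderate/severe split and time to onset, and note any adjudicated case whose candidate status or severity depended on the absolute limb.

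The cost is two lines in the SAP and a program check. A rerun and a look back at the dependent cases are needed only if the literal rule was used.

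### The SAP gives an investigator-reported differentiation syndrome event no route of its own to adjudication, and lets one event count in two symptom categories

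*SAP*

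**What the plan says.** The DS part of SAP Section VIII.B has two streams. The first is a plain count: "The number of patients with an investigator reported AE of DS will be summarized". The second is a symptom screen: "In addition, candidate cases of DS will be summarized based on AE data and also leukocyte count results from the laboratory data set".

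The screen sorts AE preferred terms into six categories: dyspnoea, pulmonary infiltrates or pleuropericardial effusion, kidney injury, hypotension, fever, and weight gain. The last four also accept a measured value (creatinine, systolic blood pressure, temperature, weight).

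The candidate rule asks for "any 2 or more AESI categories from the table above occurring concomitantly". The timing rule is: "Concomitant is defined for AESIs as AE start dates within 7 days of each other". What then goes forward is also stated: "Candidate cases will be reviewed by an adjudication committee (details are contained within a separate DS Adjudication Committee charter".

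The later summaries are built on adjudicated cases: number and percentage of patients, repeat episodes, leukocytosis, severity, time to onset, and overlap with CR or CRh. Severity follows the CTCAE grade where the investigator reported DS. Otherwise it follows a count, with severe worded in categories (more than 3) and moderate worded in AESI (2 or 3).

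The same section limits the DS analysis to IA2. Protocol Section 9.2.4.2 leaves the full method for finding candidates to the SAP.

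**The concern.** The SAP itself remarks that DS symptoms are non-specific and that the treating clinician judges them best. Yet the clinician's diagnosis does not open the way to adjudication. A site that reports the syndrome, and not two or more of its components, may produce no candidate at all.

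Protocol Section 5.5.1 treats fully developed DS as life-threatening. Because the analysis is not repeated for the final report, IA2 supplies the only planned adjudicated incidence, severity and timing. A screen that misses clinician-diagnosed cases would leave those figures incomplete.

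In the other direction, the category lists overlap. A single event could meet a rule that appears to ask for two signs.

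**Working it through.** No sample size, power or alpha is involved, so the check is to read the rule against the term lists and apply it to simple patients.

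**Step 1: is DS itself a trigger?** None of the six categories lists *Differentiation syndrome*. The reported-DS count comes first, the candidates are built as an addition to it, and no sentence joins the two streams.

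**Step 2: do terms overlap?** Exactly two preferred terms appear in more than one category:
- "Acute respiratory distress syndrome": dyspnoea, and pulmonary infiltrates or effusion.
- "Generalized oedema": pulmonary infiltrates or effusion, and weight gain.

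Repeats within a single category have no effect on the rule.

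**Step 3: apply the rule.** Count the categories reached with start dates no more than 7 days apart. A patient is a candidate if the count is at least 2. In these patients no measured value meets a criterion. The last column applies two changes: reported DS is an automatic candidate, and the two categories must come from different events.

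| AEs recorded | Categories | Candidate as written | With changes |
|---|---|---|---|
| DS only | 0 | No | Yes |
| DS and pyrexia, same day | 1 | No | Yes |
| DS and pyrexia, dyspnoea 2 days later | 2 | Yes | Yes |
| One acute respiratory distress syndrome event | 2 | Yes | No |
| One generalized oedema event | 2 | Yes | No |
| One dyspnoea event | 1 | No | No |

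**Step 4: allow for measured values.** A patient whose only AE is DS, but whose vital signs show a temperature above 38.3°C and a weight more than 5 kg from baseline, shows two categories (fever and weight gain). That patient can qualify without component AEs. Two limits remain. Concomitance is defined only by AE start dates, so the SAP does not say how measured findings are dated. Dyspnoea and pulmonary infiltrates or effusion have no measured criterion.

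**Step 5: is a reported DS with fewer than two categories realistic?** Protocol Section 5.5.1 allows DS to be recognised by any of its listed symptoms and asks for measures at the first signs, giving respiratory distress as the example. That is one SAP category. Its list also includes bone pain and dizziness, which no SAP category covers. Protocol Section 7.2.2 asks sites to fold laboratory abnormalities into the AE for the clinical syndrome where possible, so components may not be recorded as separate AEs.

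**Step 6: internal consistency.** The severity rule for adjudicated cases begins with patients who have a reported DS. The SAP therefore expects such patients in the adjudicated set but gives them no entry of their own.

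**Step 7: severity of a single-event case.** Suppose one acute respiratory distress syndrome event is adjudicated as DS and the investigator did not report DS. Counted in categories it scores 2, within the moderate range. Counted in events it scores 1, which is neither moderate nor severe. Its CTCAE grade is not used under either reading.

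**The case against.** The strongest reply is that the screen is meant to complement the investigator's diagnosis. Protocol Section 9.2.4.2 describes the candidate search as symptom-based, and reported DS is counted first in its own right. DS as a preferred term also appears in the general TEAE tables and listings. This stands: a reader might infer that clinician-diagnosed cases vanish from the safety reporting, and they do not. The gap is confined to the adjudicated tables.

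A reader might also infer that such cases can never reach the committee. The documents do not support that. The adjudication charter is not among them and could add a route, and Step 4 shows that a diagnosis-only report can still qualify through measured data. What survives is narrower: the SAP, which the protocol makes responsible for the full method, states no route for a reported DS with fewer than two categories.

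On double listing, the timing rule speaks of dates relative to each other, and the SAP says that two or more AESI can form an episode. Both suggest that separate events were intended, but neither requires them. A reader might infer that single events inflate the adjudicated incidence or are automatically graded moderate. Neither follows: the committee still reviews each candidate, and the moderate definition is worded in AESI, not categories.

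Finally, the summary of changes for SAP version 5.0 suggests that IA2 has already been performed. If so, the remedy is a reconciliation and not only an edit to the text.

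**Conclusion.** The point holds in a limited form. Under the SAP text, an investigator-reported DS with fewer than two symptom categories, whether from AEs or measured values, is not sent for adjudication. It is then absent from the adjudicated incidence, severity, recurrence, leukocytosis and onset tables. This can only lower the adjudicated count. The double listing of two terms is a lesser fault, because it mainly adds candidates for the committee to review.

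The size cannot be given in patients. The documents state neither how often DS is reported nor how often it is reported without two components. It would be tempting to apply assumed rates to the 173 evaluable patients planned for Cohort 1, but such rates would have no support in the documents, and 173 is the wrong base. The DS analysis belongs to IA2, planned at 115 efficacy-evaluable patients in Cohort 1, and safety summaries use the Safety Analysis Set.

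The conclusion assumes that the SAP is followed as written and that the charter adds no route. It merits correction because the repair is small and the adjudicated result is planned only once.

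**What to change.** In SAP Section VIII.B:

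1. State that any AE coded *Differentiation syndrome* is automatically a candidate for adjudication, whatever other categories are present.
2. State that the two categories must come from two different events or findings. If single acute respiratory distress syndrome or generalized oedema events are meant to be reviewed, say so as a deliberate rule and not as a side effect of the lists.
3. Use the same unit, categories or events, in both the severe and the moderate definitions.

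If IA2 adjudication is complete, compare the investigator-reported DS events with the candidate list, send any omitted case to the committee, and document the result in the study report. If the charter already provides a route, quote it in the SAP.

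The cost is a few sentences, a small programming change and a few more cases for the existing committee. If IA2 is closed, there is also the work of reopening adjudication for any omitted case.

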5.5.3 Hepatic Injury

Adverse events potentially associated with hepatic dysfunction have been reported in approximately 20% of patients receiving FT-2102 to date. As such, adverse events potentially associated with liver injury have been identified as Adverse Events of Special Interest (AESI). AESI, as defined in Section 7.2.4, regardless if serious or non-serious, must be reported to Forma Therapeutics Pharmacovigilance within 24 hours of knowledge of event as described in Section 7.2.4.

Patients should be monitored for any new or unusual symptoms suggestive of liver injury unrelated to the patient's primary malignancy. Symptoms may include anorexia, nausea, fatigue, right upper abdominal discomfort or vomiting, dark urine or jaundice. In the event of the development of any new clinical signs or symptoms of hepatic dysfunction, the following clinical investigation is recommended with additional action based upon the patient's clinical presentation and at the treating investigator's discretion.

a. Evaluation of international normalized ratio/prothrombin time (INR/PT), albumin, total bilirubin, direct and indirect bilirubin, amylase, lipase, AST, ALT, gamma glutamyl transpeptidase, complete blood count with differential and alkaline phosphatase

If there is evidence of new liver injury, the following actions should occur:

- a. Report the AE per Section 7.2.4
- b. Consider obtaining FT-2102 serum levels if aberrant dosing is suspected
- c. Obtain tests for viral and other infectious etiologies of hepatitis (including hepatitis A, B, C, D and E) and tests for autoimmune hepatitis
- d. Consider diagnostic imaging (hepatic ultrasound or MRI) and hepatic biopsy if the patient's clinical status permits
- e. Obtain detailed history of symptoms and concurrent or prior disease, concomitant medications including herbal and dietary supplements, alcohol use, recreational drugs (e.g., cannabidiol or tetrahydrocannabinol) and special diets
- f. Review medical history to include non-alcoholic steatohepatitis (fatty liver), cardiovascular disease, diabetes, alcoholism or autoimmune disease
- g. Evaluate and discontinue if feasible, all hepatic injury-inducing concomitant medications (prescription and over-the-counter) and other hepatic injury-inducing agents (e.g., ethanol)
- h. Consider gastrointestinal or hepatology consult

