Scatter plots presenting the maximum ALT by the concomitant total bilirubin, and the maximum AST by the concomitant total bilirubin for each patient on study (i.e., eDISH plots) will be produced. Results without concomitant bilirubin cannot be presented in eDISH plots, so the maximum value of visits which have both ALT and bilirubin (or AST and bilirubin) should be presented.

A separate summary of liver function test abnormalities will be produced, based on the FDA's guidance for industry on drug induced liver injury (June 2009), in addition to the

summaries described above. The number and percentage of patients experiencing the following abnormalities will be summarized.

	Clinical Laboratory	
Flag #	Parameter	Category
1	ALT	$>3 \times ULN; >5 \times ULN; >10 \times ULN; >20 \times ULN;$
2	AST	$>3 \times ULN; >5 \times ULN; >10 \times ULN; >20 \times ULN$
3	AST or ALT	$>3 \times ULN; >5 \times ULN; >10 \times ULN; >20 \times ULN$
4	Total Bilirubin (TBL)	$>1.5 \times ULN; \geq 2 \times ULN$
5	ALP	$>2.5 \times ULN; >5 \times ULN$
6	Concurrent AST, ALT and Total	(ALT or AST >3 x ULN) and (TBL >1.5 x ULN);
	Bilirubin	(ALT or AST >3 x ULN) and (TBL >2 x ULN);
7	Concurrent AST, ALT, Total	(AST or ALT >3 × ULN) and (TBL >1.5 × ULN) and ALP <2 x ULN;
	Bilirubin, without ALP abnormality	(AST or ALT >3 × ULN) and (TBL >2 × ULN) and ALP <2 x ULN;
8	ALT>3x ULN or AST>3x ULN	(ALT >3x ULN) or (AST >3x ULN) and with TEAEs* starting +/- 7
	with concurrent report of	days of the lab sample
	selected TEAEs during study*	

*Selected TEAEs include nausea, vomiting, anorexia, abdominal pain, abdominal discomfort, fatigue, jaundice, pruritus, chromaturia, and faeces discoloured.

The flags in the table above are only applied for post-baseline values. For flag #6, if ALT or AST is elevated > 3x ULN, all total bilirubin results within 7 days of the result should be considered. If Flag #6 is applied and ALP is <2x ULN for all samples drawn within +/-7 days of the AST, ALT, bilirubin sample, then Flag #7 will be applied. Flag #8 requires the adverse event start date to occur within +/-7 days of an AST/ ALT value exceeding 3x ULN.

D. Vital Signs

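### The eDISH plots pair peak ALT or AST with same-visit bilirubin, so they can show fewer combined elevations than the SAP's own 7-day Flag #6 count

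*SAP*

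**What the plan says.** SAP Section VIII.C, under the evaluation of liver function tests, plans one scatter plot for ALT and one for AST, with one point per patient. The first is "Scatter plots presenting the maximum ALT by the concomitant total bilirubin"; the second is the "maximum AST by the concomitant total bilirubin for each patient on study (i.e., eDISH plots) will be produced". The SAP then explains the pairing. A transaminase result that has no bilirubin to go with it is left off the plot, and the choice of value is limited accordingly: "so the maximum value of visits which have both ALT and bilirubin (or AST and bilirubin) should be presented". No day window is given for the plot, and no peak bilirubin is used.

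The table of liver test abnormalities that follows applies another rule: "For flag #6, if ALT or AST is elevated > 3x ULN, all total bilirubin results within 7 days of the result should be considered". Flag #6 combines ALT or AST above 3x ULN with total bilirubin above 1.5x and, separately, above 2x ULN. Flag #7 adds ALP below 2x ULN, with a window of 7 days either side. All flags use post-baseline values only.

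Protocol Section 5.5.3 gives the clinical background: "Adverse events potentially associated with hepatic dysfunction have been reported in approximately 20% of patients receiving FT-2102 to date". These events are classed as adverse events of special interest.

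**The concern.** An eDISH figure is read for patients who have raised transaminases and raised bilirubin together. ALT or AST above 3x with bilirubin above 2x ULN also forms the core of one of the permanent-discontinuation rows in Protocol Table 7, so this is the part of the plot that readers will look at first.

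Two outputs in one SAP section address the same question with different definitions of concurrency. If bilirubin peaks later than ALT, the single plotted point is fixed at the ALT peak, and the later pair that meets Flag #6 is never drawn. A reader of the figure could then see fewer combined elevations than the adjoining table reports. In addition, if a patient's true maximum ALT or AST was drawn without bilirubin, the rule replaces it with a lower paired value.

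The setting makes later bilirubin results likely to exist. Protocol Appendix 1 schedules serum chemistries on Days 1, 5, 8, 12, 15, 19, 22 and 26 of Cycle 1, and Section 5.5.3 asks for liver tests at least twice weekly after new liver injury.

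**Working it through.** The plan states no figure to reproduce, so the check applies the two rules to the same data. All values are multiples of ULN.

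**Rules**

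- Plot: among visits with both tests, find the visit v with the highest ALT and draw (ALT at v, bilirubin at v).
- Flag #6, upper category: some ALT or AST above 3 on day s and some bilirubin above 2 on day t, with t and s no more than 7 days apart.

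**Direction of disagreement.** If a plotted post-baseline point has ALT above 3 and bilirubin above 2, both come from one visit, so t − s = 0 and Flag #6 is met. The converse fails. Suppose Day 15 shows ALT 12 and bilirubin 1.2, and Day 19 shows ALT 6 and bilirubin 3. The plot draws (12, 1.2). Flag #6 is met, because ALT exceeds 3 and bilirubin exceeds 2 on Day 19 (and Day 19 is only 19 − 15 = 4 days from the Day 15 ALT).

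**Assumed timelines.** In A to D the ALT peak is 8 with bilirubin 0.8 at that visit, followed by the later pair shown. In E both tests are raised at the peak visit.

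| Case | Later pair | Plotted now | Flag #6 (>2x) | Peak ALT with highest bilirubin within 7 days | Peak against peak |
|---|---|---|---|---|---|
| A | +4 days: ALT 6, bilirubin 2.5 | (8, 0.8) | yes | (8, 2.5) | (8, 2.5) |
| B | +7 days: ALT 2.5, bilirubin 2.5 | (8, 0.8) | yes | (8, 2.5) | (8, 2.5) |
| C | +10 days: ALT 2.5, bilirubin 2.5 | (8, 0.8) | no | (8, 0.8) | (8, 2.5) |
| D | +10 days: ALT 4, bilirubin 2.5 | (8, 0.8) | yes | (8, 0.8) | (8, 2.5) |
| E | none (peak visit: ALT 8, bilirubin 2.5) | (8, 2.5) | yes | (8, 2.5) | (8, 2.5) |

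The present rule disagrees with Flag #6 in A, B and D. A 7-day window around the ALT peak repairs A and B but not D. Peak against peak places every Flag #6 patient in the upper-right region of at least one of the two plots: the flag requires some ALT or AST above 3 and some bilirubin above 2, so the corresponding peaks are at least as high. It also brings in C, which Flag #6 does not count.

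**Illustrative size.** The documents give no lag between the ALT and bilirubin peaks, so any percentage is conditional on assumptions. The base set-up took ALT peaks of 5–25x, bilirubin peaks of 2.2–8x, exponential rise and fall with time constants of 4 and 8 days, and sampling every 3.5 or 7 days. The first row spans repeat runs of that set-up, in which baseline levels and visit phase were also free choices. Entries are the share of Flag #6 patients plotted outside the >3x and >2x region.

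| Setting | Lag 0–3 days | Lag 0–7 days | Lag 3–10 days |
|---|---|---|---|
| Base | 4–9% | 24–38% | 58–76% |
| Time constants 8 and 12 days | about 2% | 9–11% | 25–30% |
| Bilirubin peaks 4–10x | at most 1% | about 15% | 47–54% |

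With zero lag the share is 0%.

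**The case against.** The strongest reply is that no case disappears. Directly below the plot the SAP tabulates Flags #6 and #7, Flag #4 counts raised bilirubin alone, the shift tables use the worst post-baseline value including unscheduled visits, and all laboratory results are listed. No test, stopping rule or decision in the SAP uses the figure. This stands, and it rules out a reading that a reader might otherwise reach, namely that liver cases are missing from the safety report.

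The SAP also draws no quadrant: the 3x and 2x limits used here are borrowed from Flag #6. Nor does it formally define concomitant for this plot, and for differentiation syndrome it uses 7 days. Both observations are correct. The second does not rescue the plot, because the reference to visits with both tests points to same-visit pairing and the 7-day definition is not carried over.

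Finally, peak against peak ignores timing and creates its own mismatch, as case C shows. That is a real cost, and it is why the proposed figure needs a symbol for the flagged patients.

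**Conclusion.** The concern holds as a limited inconsistency. The plot and Flag #6 use different concurrency rules, the SAP does not reconcile them, and for post-baseline values the figure can only under-show combined elevation relative to the table. The defect affects a descriptive safety figure and its agreement with the adjoining counts.

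The conclusion rests on the same-visit reading of the plot rule and on the Flag #6 cut-offs as the region of interest. The number of patients affected cannot be derived from the documents. The simulated shares run from 0% to 76% according to lag, decay and peak assumptions, and should not be quoted as expected values.

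Two stronger statements might be inferred and are not supported. It does not follow that every patient with a later bilirubin rise is plotted outside the region; under short lags few are. Nor do the documents make liver injury the main toxicity of FT-2102: they give a frequency of about 20% and special-interest status, but differentiation syndrome is also of special interest in the SAP and has its own adjudication committee.

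**What to change.** In SAP Section VIII.C, redefine the two figures as each patient's peak post-baseline ALT (and, separately, AST) against peak post-baseline total bilirubin, both in multiples of ULN. Delete the same-visit requirement, which also restores any maximum that lacks a paired bilirubin. Add reference lines at 3x ULN for the transaminase and 2x ULN for bilirubin. Use a distinct symbol for patients who meet Flag #6 or #7 under the existing 7-day rule.

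The cost is a short SAP edit and a changed plotting variable; no new data are needed. The downside is that some temporally unrelated bilirubin rises will move into the upper-right region, where the symbol separates them from flagged patients.

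If the sponsor prefers to keep the present axes, the minimum is to mark Flag #6 and #7 patients on the existing plot, so that figure and table can be reconciled.
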